5.4.4. Follow-up of excluded subjects

If no dose of the investigational product/comparator product was received by the patient and the patient withdrew from the trial for any reason, he/she is not followed up further and

his/her data are not included in the statistical analysis.

If the investigational product/comparator product was received by the patient and the patient is withdrawn from the trial for any reason unrelated to the development of an AE, including failure to attend the next visit for an unknown reason, the investigator should contact the patient and schedule a date for the patient's end-of-trial visit.

If SAEs occur, the patient should be monitored by a physician according to the AE surveillance guidelines.

Follow-up of excluded patients due to the development of AE/SAE will be carried out until resolution or stabilization of AE/SAE-induced manifestations.

6. Trial design

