8.3. AE recording and reporting

Adverse events (AEs)

The protocol provides for the recording of all AEs that occur to the patient after the first administration of the trial therapy and until the end of the patient's participation in the trial.

During screening, information about medical adverse events will be attributed to the patient's medical history (pre-existing/concomitant conditions).

The planned trial will record all deviations in the health status of patients (based on the results of physical examination, laboratory and instrumental methods of investigation) from the data obtained at the Screening and from the accepted reference values.

After obtaining the necessary information, the investigating physician will categorise the patient's condition as 'normal', 'clinically insignificant abnormalities' or 'clinically significant abnormalities'. In case the abnormalities detected during the trial have not been previously reported, or there is an aggravation of the patient's condition vs. the data obtained at Screening, the detected abnormalities will be classified as AEs.

If the abnormalities detected during the trial have been recorded at Screening and there is no significant negative trend in the reasonable opinion of the investigator, the detected abnormalities will be classified as clinically insignificant abnormalities (CIA).

All detected abnormalities, irrespective of whether they are attributed to AE or CIA, will be analysed when reporting the results of the clinical trial.

An adverse event is defined as any adverse change in the health status of a patient or subject of a clinical trial/trial to whom a medicinal product has been administered, irrespective of the causal relationship with its use.

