9.6. Population to be analysed

The following population groups will be used for the analyses:

1. The ITT (Intent-to-treat) population will include all randomized patients regardless of investigational product/placebo administration.
2. The mITT (modified Intent-to-treat) population will include patients who have completed the full course of therapy, regardless of the presence of Protocol violations/ deviations.
3. The PP (Per protocol) population will include patients who completed the trial in accordance with the Protocol.

At the stage of statistical data processing, additional analyses of the efficacy and/or safety of investigational product/placebo in subpopulations of patients of different age groups can be performed.

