Interval (quantitative) data will be described using: arithmetic mean, standard deviation, median, lower (25%) and upper (75%) quartiles, minimum, maximum and coefficient of variation. Categorical (qualitative) data will be described using frequencies, percentages and/or fractions.

To compare quantitative data distributed according to the normal distribution law, it is planned to use standard parametric criteria: Student's t-test for dependent/independent samples, analysis of variance (ANOVA) for repeated measures.

It is planned to use standard nonparametric criteria to compare quantitative data distributed according to a law other than normal: Mann-Whitney U-test, Wilcoxon T-test, Friedman's criterion.

The test for conformity to the normal law of distribution will be carried out using the Shapiro-Wilk test.

Comparisons of frequencies of indicators between treatment groups will be made using Pearson's χ^2 test or Fisher's exact test.

9.7.3. Statistical methods for assessing the safety of using the investigational product and the comparator product

Safety parameters will be analysed in the ITT population.

Safety data will be analysed using the methods outlined for the application of the efficacy data assessment. Analyses of AEs will be performed based on an assessment of the incidence of adverse events / serious adverse events. Adverse events reported during the course of the trial will be presented by frequency (number of patients with AEs and number of such AEs in the group). AEs will also be presented by severity and relationship to investigational product

administration. Comparison of the number of patients with AE between therapy groups will be performed using Fisher's exact test or Pearson's χ^2 test.

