Safety assessment will be carried out based on the analysis of the frequency of occurrence of all adverse events, dynamics of laboratory and instrumental parameters.

AEs are recorded after the first use of the drug until the patient completes the trial and are tracked throughout the trial until they are resolved/stabilised.

Frequency tables with data on discontinuation of therapy or changes in therapy parameters due to AEs will be presented.

Pre- and post-trial data will be compared to assess safety parameters.

All data will be analyzed on the safety population. Regardless of the reason for trial termination, data from all included patients will be included in the safety analyses of the trial therapy.

Adverse event (AE) is any adverse change in the health status of a patient or subject of a clinical trial to whom a medicinal (investigational) product has been administered, regardless of the causal relationship with its use.

Serious adverse event (SAE) - any adverse medical event that, regardless of the dose of the medicinal product, has resulted in death, is life threatening, requires hospitalization or its prolongation, has resulted in permanent or significant disability or impairment, is a congenital anomaly or birth defect or other medically significant event.

Adverse reaction (AR) - unintentional adverse body reaction associated with the use of a medicinal product/investigational product, suggesting at least a possible relationship with the use of a suspected medicinal product/investigational product.

Unexpected adverse reaction (UAE) - an adverse reaction, the nature, severity or outcome of which does not correspond to the information in the current instructions for medical use of the medicinal product or in the investigator's leaflet for an unregistered medicinal product.

Serious unexpected adverse reaction (SUAR) - an unexpected adverse reaction that is characterized by features of a SAE.

The parameters of the AE/SAE will be estimated as follows:

Severity of AEs:

The investigator assesses the severity of an adverse event according to the Common Terminology Criteria for Adverse Events (CTCAE) current version at the time of the trial. If an adverse event cannot be classified according to the CTCAE criteria, the Investigator will select the closest description of the severity of the adverse event from those given in the classification based on personal clinical experience:

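### Safety is assigned to all randomised patients, another clause drops undosed withdrawals from the analysis, and the SAP's safety population is never defined

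*Protocol*

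**What the plan says.** **Which set is used for safety.** Protocol 9.7.3 says "Safety parameters will be analysed in the ITT population"; the synopsis and SAP section 11 repeat it. Under Protocol 9.6 the ITT set "will include all randomized patients regardless of investigational product/placebo administration", and SAP section 11 gives an equivalent definition.

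**Undosed patients.** Protocol 5.4.4 sets the condition "If no dose of the investigational product/comparator product was received by the patient and the patient withdrew from the trial for any reason". Such a patient is not followed further, and "his/her data are not included in the statistical analysis".

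**A further label.** SAP section 10 says "All data will be analyzed on the safety population". The lists of analysis sets in Protocol 9.6 (ITT, mITT, PP) and SAP section 11 (the same three plus a pharmacodynamic subset) contain no set of that name. The next sentence in SAP section 10 adds that "data from all included patients will be included in the safety analyses of the trial therapy", without mentioning dosing or treatment received.

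**When events are collected.** Protocol 8.3: "The protocol provides for the recording of all AEs that occur to the patient after the first administration of the trial therapy". SAP section 10 likewise tabulates events after the first dose.

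**Attribution.** Protocol 11.8 lists giving one patient product under different randomisation codes, and mismatches between labelling and code, among its examples of significant deviations. Neither document says which arm such a patient's events belong to.

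**The concern.** Take a patient who is randomised, never dosed and withdraws. Protocol 9.6, Protocol 9.7.3 and SAP section 11 keep that patient in the safety denominator; Protocol 5.4.4 removes the patient; SAP section 10 does not settle it. Such patients can arise: Protocol 4.3.2 places randomisation before the product is prescribed, Protocol 5.3 foresees infection results that arrive after randomisation and lead to exclusion, and 5.4.4 itself plans for withdrawal without a dose.

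Under the ITT rule this patient can enter the denominator of an AE proportion but never the numerator. Comparing the frequency and severity of adverse events is one of the trial's two main objectives. The denominator should therefore be fixed in advance, not chosen among conflicting sentences once the data are in. The same clause in 5.4.4 also contradicts the ITT definition used for the supporting efficacy analysis.

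**Working it through.** **The plan's own figure.** The plan gives no number for the safety set, so the denominator comes from the sample size in Protocol 9.1. With one-sided α = 0.05, 80% power, ε − δ = 0.292 − 0.027 = 0.265 and σ = 0.802:

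n = 2 × (1.6449 + 0.8416)² × 0.802² / 0.265² = 113.25, rounded up to 114 per group, or 228 in total. This matches. The 304 randomised corresponds to 228 / 0.75, and 1:1 allocation gives 152 per arm.

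**Dilution.** Let *u* be the number randomised but never dosed in an arm (not in the documents; assumed) and *p* the AE proportion among dosed patients. No event is recorded before the first dose, so

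reported ITT proportion = p × (152 − u) / 152.

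Each undosed patient costs 1/152 = 0.66% relative. For a reference rate I take the previous trial (EPICA; Protocol 2.3.2): 32 patients with events out of 150, or 21.3%, both arms together.

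| u per arm (assumed) | dosed | reported if p = 21.3% | relative loss |
|---|---|---|---|
| 1 | 151 | 21.2% | 0.7% |
| 3 | 149 | 20.9% | 2.0% |
| 8 | 144 | 20.2% | 5.3% |
| 15 | 137 | 19.2% | 9.9% |

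In round figures, an assumed 20% rate with 1% undosed becomes 0.20 × 0.99 = 19.8%, and with 5% undosed 0.20 × 0.95 = 19.0%.

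**Effect on the comparison.** The relative risk (drug to placebo) is multiplied by (152 − u_drug) / (152 − u_placebo). If the two numbers are equal, the factor is 1. With 8 undosed on drug and none on placebo it is 144/152 = 0.947; with the reverse it is 152/144 = 1.056.

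**Attribution, if events were counted by randomised arm.** Assume true rates of 30% and 20%, and *m* patients per arm who received the other treatment. The observed difference is 10 × (152 − 2m) / 152 points: 9.87 for m = 1, 9.61 for m = 3 and 8.95 for m = 8. The rates and m are assumptions; the documents give no frequency of such errors.

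**Use of the term ITT.** Protocol 9.1 describes the EPICA ITT set as patients dosed at least once, which is not the definition in Protocol 9.6. The term has two meanings within one protocol.

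**The case against.** **There are two rules, not three.** A reader might count three incompatible safety sets. The documents do not support that. The sentence after the safety-population statement in SAP section 10 speaks of all included patients, and SAP section 11 then names ITT. The safety population is best read as an undefined label leaning towards ITT. What stands is that it is undefined.

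**Counting by randomised arm is not stated.** A reader might infer that a patient given the wrong product will have drug events counted under placebo. ITT usually implies the randomised arm, but no sentence says so for safety. The SAP templates lean the other way: Table 19 is headed by what was administered, and Table 31 counts events after each product is taken. A different randomisation code also need not mean a different arm. What stands is that attribution is left open.

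**The direction of bias is not fixed.** It is tempting to say that the drug is made to look safer. Equal dilution lowers both rates and leaves the relative risk unchanged, and more undosed patients on placebo would make the drug look worse by comparison. Misattribution hides harm only if the drug does raise event rates.

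**Few patients are affected.** Randomisation and first dose are both at Visit 1, in hospital inpatients, so the upper rows of the table are more plausible than the lower ones. If 5.4.4 is applied there is no dilution from undosed withdrawals, and the result comes close to a dosed-patients set. That clause is also not limited to randomised patients, so part of it may concern withdrawals before randomisation. This reduces the size of the problem. It does not remove the contradiction, because nothing says which rule prevails.

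**Conclusion.** The point holds as a conflict of definitions with a small numerical effect. Safety in an ITT set that includes undosed patients cannot be reconciled with a clause that takes undosed withdrawals out of the analysis. The SAP's safety population has no definition, and the rule for attributing events to treatment is missing. Under the ITT rule the AE proportion in an arm can only fall, by 0.66% relative per undosed patient. On the assumed 1–5% undosed and 20% rate, that is 0.2 to 1.0 percentage points, and probably towards the low end. The effect on the relative risk is nil if dilution is equal and can go either way if it is not. The sample size and the primary per-protocol test are unaffected. The documents do not support a claim that events will be credited to the wrong arm or that the drug will systematically look safer.

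**What to change.** - Define one safety set in Protocol 9.6 and SAP section 11: all randomised patients who received at least one dose, analysed by treatment actually received.
- Use that set by name in the synopsis, Protocol 9.7.3 and SAP section 10, in place of ITT and of the undefined label.
- Reword the data clause in Protocol 5.4.4 so that undosed patients are left out of the safety set but stay in the ITT set as 9.6 defines it.

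The last change restores these patients to the ITT count only. They are not followed up under 5.4.4, and missing data are not filled in (Protocol 9.4, SAP section 11), so it supplies no Day 71 mRS for them.

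The cost is a few sentences in each document. The SAP is still written for protocol version 1.3 while the protocol is at version 1.5, so the change can go into a SAP update that is needed anyway.

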9.8. Significance level and power of the criterion

The level of significance (genus I error α) was chosen to be 0.05 (5%) and the power of the criterion was chosen to be at least 0.8 (80%).

Since an interim data analysis is planned, a genus I error correction approach α ($\alpha = 0.0294$)¹ will be used to prove the hypothesis of "superiority" of investigational product therapy over placebo therapy on the primary efficacy criterion.

9.9. Statistical criteria for trial discontinuation

In the first phase, at the end of the trial, all randomized patients (304 patients) will undergo an interim analysis of the data for the primary endpoint²:

- If the required power $\geq 80\%$ is achieved, a 95% one-sided confidence interval for the difference in values of the primary efficacy criterion ($\mu_t - \mu_p$) will be used to prove the hypothesis of 'superiority'; the results obtained will be analysed and used to write the final clinical trial report.
- If the calculated power is less than 80 per cent, the sample size will be recalculated based on the data obtained after the first stage to achieve a trial power of 80 per cent, using a correction for genus I error α ($\alpha = 0.0294$). A protocol amendment will then be submitted to the Ministry of Health and, once approval is granted, the necessary additional number of patients will be enrolled, followed by pooling of all data for final analysis and writing of the final clinical trial report. A 97.06% one-sided confidence interval for the difference in values of the primary efficacy criterion ($\mu_t - \mu_p$) constructed from pooled patient data, i.e. obtained from the first and second stage results, using $\alpha = 0.0294$, will be used to prove the hypothesis of 'superiority'. The final clinical trial report will be written using data from all patients.

